## 1. Background and Significance

Patient compliance with laboratory testing is one of the most underrecognized challenges in developing a treatment plan for acute and chronically ill patients. The ability to offer alternatives to standard venipuncture blood draws would greatly increase a laboratory's ability to provide testing to patients and health care providers.

Currently the venipuncture in the antecubital fossa area is the standard procedure for blood collection. Unfortunately, this can be painful and the veins in this area could be hard to access in some patients (including kids).

The fingerstick blood draw has been used as an alternative for calcium and glucose measurements. Capillary blood is used in neonatal population as well.

The procedure of finger-prick blood collection may in some instances cause minor levels of stress and anxiety to individuals as well as acute levels of pain at the time of "prick." We are attempting to reduce stress and anxiety with this new device that aims to avoid the pain of this procedure.

Aiming a less painful, potentially easier alternative we devised a novel that can be applied distally on the digit prior to the blood collection procedure and may provide analgesia through propylene glycol, a liquid coolant that is run through tubes in the device to safely cool tissue to 0°C to 7.5°C to achieve numbing. We hypothesize that this device will safely and effectively reduce the pain associated with the fingertip pricks and increase the amount of capillary blood collected. Besides, we believe in the future this novel could be used for other finger or procedures of the nail unit.

Multiple punctures with a large lancet were a frequent cause of discomfort among patients and should be given consideration since the desire to avoid a painful venipuncture is a common reason given as justification to consider this type of sample. With this new device the discomfort will be reduced by its application followed by the numbness of the finger.

Therefore, capillary sampling should be considered on patients who refuse venipuncture or venous access cannot be established. This method is also considered to be useful for screening of blood disorders.

Iwasawa et al reached a good correlation observed between fingertip and venous blood test values for the 14 biochemical parameters. For example, there was no significant difference in the white blood cells count across specimens, and the fingertip blood collection method allowed them to collect specimens by a single puncture, obtaining consistent results for the blood cell counts.

The study will take place at MGH's Clinical Unit for Research Trials & Outcomes in Skin (CURTIS) at [name], or Translational Clinical Research Center (TCRC) on the 12th floor of the White Building.

## **2. Specific Aims and Objectives**

To evaluate a novel tissue-cooling device for pain management during needle sticks and /or blood draw on the fingertips.

The study will use a device developed in conjunction with Sunrise Labs, an experienced medical device development firm (<https://www.sunriselabs.com/>).

The specific aims of the study are as follows:

Aim 1. Evaluate the pain management capability of the tissue-cooling device for finger prick blood draws compared to standard of care (antecubital venipuncture).

Aim 2. Quantify the amount of blood collected by the finger pricks.

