## **3. General Description of Study Design**

This is a self-controlled single-site study of 12 healthy subjects. The novel Cooling Device for Pain Management will be applied to the subject's finger, and a blood draw will be performed. The study includes blood amount quantification and a pain score report to evaluate the pain caused by the prick. Study subjects will be asked to do one visit of approximately 1 hour.

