#### *Visit 1*

Visit 1 is expected to last approximately 1 hour.

The following assessments will be performed during Visit 1:

- Review of eligibility criteria
  - Ring size measurement
- Review of medical history and medications
  - Urine pregnancy test (for female participants of childbearing potential)
- Take blood pressure (2 times before treatment; 2 times after) using a standard hospital owned blood pressure arm cuff device.
- The novel digit cooling device will be turned on and allowed to chill to -3 degrees Celsius prior to the procedure.
- Two fingers (one on each hand) will be pricked during Visit 1: the “control” digit and the “chiller” digit.
  - The first finger to be pricked will be randomized.
  - The pricked fingers will be either the fifth or third digit(s).

- Pricks will be administered using a sterile and disposable McKesson Push-Button 17G or 23G Safety Lancet, bought specifically for this trial.
- Subjects will be instructed on how to report a pain score for each prick. A visual 10-point pain scale will be used (see below).
- The procedure for the “control” digit is as follows:
  - A Beurer oximeter will be used to measure the percent oxygen and pulse rate.
  - A thermal camera will be used to measure the temperature of the finger tip.
  - One prick will be applied to the ventral tip of the “control” digit. A pain score will be reported by the subject.
  - The pricked finger will subsequently be held over a single-use Whatman 903 filter paper. Approximately every ten seconds after the prick, the filter paper will be gently applied to the blood drop to absorb the blood. This will be repeated on new locations of the filter paper until blood flow stops. At least one Whatman 903 filter paper will be used per finger prick. The Whatman 903 filter paper will be imaged.
- The procedure for the “chiller” digit is as follows:
  - A sterile glove will be placed on the “chiller” hand. The top of the fifth or third finger of the glove will be cut and rolled down to the base of the finger to promote venostasis and blood harvesting.
  - A Beurer oximeter will be used to ensure there is not enough blood flow to measure the percent oxygen and pulse rate in the finger.
  - A thermal camera will be used to measure the temperature of the finger tip.
  - A layer of glycerol will be applied circumferentially to the intended treatment area on the “chiller” digit.

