  - No more than one minute after sterile glove application, the novel digit cooling device will be applied to the “chiller” digit on the area with glycerol.
  - No more than four minutes after the novel digit cooling device is applied to the “chiller” finger, one prick will be applied to the ventral tip of the “chiller” digit. A pain score will be reported by the subject.
  - The pricked finger will subsequently be held over a single-use Whatman 903 filter paper. Approximately every ten seconds after the prick, the filter paper will be gently applied to the blood drop to absorb the blood. This will be repeated on new locations of the filter paper until blood flow stops. At least one Whatman 903 filter paper will be used per finger prick. The Whatman 903 filter paper will be imaged.
- Post-procedure images will be taken of the tips of the “control” and “chiller” digits.
- A thermal camera will be used to video record the fingers starting with the sterile glove application on the “chiller” finger until the post-procedure images have been collected by an encrypted iPhone 12 Pro.
- Regular video recording with an encrypted iPhone 12 Pro will be done simultaneously.

Wong-baker pain assessment on a visual analog pain scale:

©1983 Wong-Baker FACES Foundation. [www.WongBakerFACES.org](http://www.WongBakerFACES.org)  
Used with permission. Originally published in *Whaley & Wong's Nursing Care of Infants and Children*. ©Elsevier Inc.

- The device will be removed from the digit
- Study staff will document any anticipated side effects or Adverse Events that occur during the study visit.
- A licensed physician investigator will be operating the study device during the procedure.

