#### **Devices to be used**

#### **Experimental Cooling Device description**

The experimental device is a cooling device intended to provide analgesia during needle sticks for blood draws on digits extremities. The device is a circulating fluid chiller using a propylene glycol / water mixture (4:7) flowing through an applicator designed to cool the conductive nerves in the digit to a temperature below which nerve conduction from the distal portion of the digit reduces and/or ceases. The device is designed with two u-shaped coolant tubes that are applied to the circumference of tissue at the base of a digit. The coolant tubes appose each other to surround the digit and then are brought together with a screw /spring mechanism to apply sufficient pressure to the main arteries feeding the digit to partially occlude blood flow, thereby enhancing the tissue-cooling effect.

The clinician monitors tissue blanching while applying the applicator to ensure there is sufficient but not excessive occlusion.

With a circulating coolant temperature of -3°C, the device will cool tissue in contact with and near proximity to the cooling tubes to 0°C to 7.5°C. The subject's hand will be wearing an sterile glove to provide a barrier between the cooling ring and skin. The fifth finger of the glove will be removed sufficiently to expose the area to be pricked in this study. This circumferential ring of cold and partially occlusive pressure on the digit will provide analgesia by blocking nerve conduction signals from leaving the digit and signaling pain to the central nervous system. The pressure on the arterial vessels assists tissue cooling by reducing blood flow and therefore the amount of heat transferred to the cooled tissue.

This device poses no risk to the subject if left on for 10 minutes or less. The device will only be on the subject for 7 minutes, and glycerol will also be used to further decrease any risk to the subject.

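### Aim 1 names antecubital venipuncture as the pain comparator, but the study performs, scores and analyses only finger pricks

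*Combined protocol and SAP*

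**What the plan says.** Section 2 states Aim 1 as "Evaluate the pain management capability of the tissue-cooling device for finger prick blood draws compared to standard of care (antecubital venipuncture".

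Section 1 gives a different contrast: "We hypothesize that this device will safely and effectively reduce the pain associated with the fingertip pricks". Section 3 describes a self-controlled study with "a pain score report to evaluate the pain caused by the prick". In section 6.a, "Two fingers (one on each hand) will be pricked during Visit 1", one called the control digit and the other the chiller digit. Each receives one lancet prick followed by one pain score.

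The chiller digit is prepared in ways that the control digit is not. The finger of a sterile glove is "cut and rolled down to the base of the finger to promote venostasis and blood harvesting", and "A layer of glycerol will be applied circumferentially to the intended treatment area" before the cooling device goes on. The device description attributes the pain relief to the device's own two actions: a "circumferential ring of cold and partially occlusive pressure on the digit will provide analgesia".

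Section 9 makes the Wong-Baker score the primary clinical outcome. It describes pain by hand and tests control scores against experimental scores.

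**The concern.** An aim fixes the comparison that the trial may report. Aim 1 promises a comparison with venipuncture, and the study collects no venipuncture pain data. A cooled finger prick may well hurt less than an uncooled one, but that says nothing about whether either hurts less than an antecubital draw.

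The risk of a wrong claim is real because section 1 presents the device as a way round painful venipuncture. A favourable difference between hands, filed under Aim 1, could easily be read as less pain than standard of care, and no data would support that reading.

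A smaller point concerns what the two-hand contrast does estimate. The glove and glycerol are used only on the chiller side. The difference therefore belongs to the whole chiller-digit procedure and cannot be credited to cooling alone.

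**Working it through.** The plan gives no figure of its own on this point, so the check sets the sections side by side and counts the scores.

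**Step 1. Trace the comparator through the protocol.**

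| Section | Content relevant to pain | Venipuncture? |
|---|---|---|
| 1. Background and Significance | Motivation; hypothesis about fingertip-prick pain | Context only |
| 2. Aims, opening objective | Pain control for procedures on the fingertips | No |
| 2. Aims, Aim 1 | Device compared with standard of care | Yes, as comparator |
| 3. Study design | Pain score for the prick | No |
| 6.a Visit 1 | Two lancet pricks, one per hand, each scored | No |
| 6.b Data to be collected | Pain scores, oximetry, video, photographs, filter-paper images | No |
| 7.a Risks | Complications of the prick | No |
| 9. Statistical Analysis | Hand against hand; control against experimental | No |

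**Step 2. Count the word.** In the supplied text, venipuncture occurs 4 times in the section 1 background, once in Aim 1, and 0 times from section 3 to the end of the reference list.

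**Step 3. Count the pain scores.** Inputs from section 6.a: 1 score for the control-digit prick and 1 for the chiller-digit prick, where "one prick will be applied to the ventral tip of the" chiller digit once the device is in place.

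- Scores per subject = 1 + 1 = 2.
- Venipuncture scores per subject = 0.
- With the 12 subjects of sections 3 and 4: 2 × 12 = 24 pain scores, of which 0 × 12 = 0 are for venipuncture.
- With the 16 subjects named in section 9: 2 × 16 = 32 scores, of which 0 × 16 = 0 are for venipuncture.

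The venipuncture count is zero at either sample size. Which of the two sizes applies, and how 16 was obtained, are separate questions with no bearing here.

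**Step 4. Look for an indirect route.** Section 3 says that blood will be drawn, but the same sentence first puts the device on the finger and the next sentence speaks of the prick. It describes the finger-prick sample. No historical or external venipuncture pain value is given or planned, so an indirect comparison is not available either.

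**Step 5. Identify which text is out of line.** The opening objective of section 2, the hypothesis in section 1, the design, the procedures, the data list and the analysis all concern finger pricks. Only the comparator clause of Aim 1 does not.

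**Step 6. Compare the two digits.** Both get oximetry, a fingertip temperature reading, one prick and blood collection on filter paper. The chiller digit also gets the rolled glove, the glycerol and the device. The control-digit procedure lists none of these three.

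**The case against.** The contradiction itself is hard to dispute; the case against concerns its weight.

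- **It is one clause, and the operative contrast is clear elsewhere.** Sections 6.a and 9 leave no doubt that control and chiller digits are compared, the remedy changes no estimate, and section 9 does not plan to report a venipuncture comparison. This is true, and it is why the fix is cheap. It does not lower the importance: the clause defines the claim attached to the primary outcome, and the design cannot support that claim.
- **The sponsor's intent is not stated.** Section 1 motivates the device as an alternative to venipuncture, so that contrast may have been wanted. This stands as a reason to put both routes to the sponsor. The weight of the text still points to the finger-prick contrast.
- **Glove and glycerol are part of using the device.** The device description presents the glove as a skin barrier and the glycerol as a safety measure, so device against no device is a legitimate contrast. Agreed. But section 6.a also gives the rolled glove the purpose of venostasis, so describing the result as that of the whole procedure is the accurate wording. The main finding does not depend on this point.

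**Conclusion.** The concern holds and should be corrected before the results are reported. Aim 1 states a comparison for which the study collects no data: 0 of 2 pain scores per subject, whatever the number of subjects and whatever the test. What the design can estimate is the difference in finger-prick pain between the chiller-digit procedure as a whole and a prick on the other hand without it.

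The conclusion rests on the supplied text. The sections on design, procedures, data and analysis show no gap or redaction where a venipuncture step could have stood. It needs no assumption about effect size or variability.

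**What to change.** Reconcile Aim 1 with sections 6.a, 6.b and 9 by restating it, for example:

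*Evaluate finger-prick pain with the cooling-device procedure as applied to the chiller digit (section 6.a, Visit 1), compared with a finger prick without that procedure on the subject's other hand.*

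Two reporting rules follow. Do not present the two-hand result as a comparison with venipuncture or with standard of care. Describe it as the effect of the whole chiller-digit procedure, including glove and glycerol, and not of cooling alone.

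**Cost.** Protocol wording only, with no new procedure, data item or test. The price is a narrower claim that is silent on venipuncture.

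**Alternative.** If the sponsor does intend the venipuncture contrast, rewording is not enough. The procedure, its pain score, the data item and the analysis are all absent and would have to be added, which costs considerably more.

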## **3. General Description of Study Design**

This is a self-controlled single-site study of 12 healthy subjects. The novel Cooling Device for Pain Management will be applied to the subject's finger, and a blood draw will be performed. The study includes blood amount quantification and a pain score report to evaluate the pain caused by the prick. Study subjects will be asked to do one visit of approximately 1 hour.

## **4. Subject Selection**

Subjects will be screened to determine if they meet all the eligibility criteria specified below.

We will recruit and screen up to 20 subjects with the goal of having 12 subjects enroll and complete the study.

### **a. Inclusion/Exclusion Criteria**

Inclusion Criteria:

- Signed informed consent to participate in the study.
- Male or Female subjects,  $\geq 18$  and  $\leq 60$  years of age at the time of enrollment.
- All Fitzpatrick Skin Types are eligible
- General good health confirmed by medical history and skin examination of the area to be treated
- Subjects fifth finger is 13-23mm in diameter at the distal phalanges.
  - Subject must be able to read and understand English.

Exclusion Criteria:

- Subject has had a surgical procedure(s) in the intended area of treatment in the last 6 months.

- Sensitivity to the cold or history of cold-induced diseases including Raynaud's disease and cryoglobulinemia
- Subject has a history of bleeding disorder or is taking any medication that in the investigator's opinion may increase the subject's risk of bruising.
- Suffering from significant skin conditions in treatment areas or inflammatory skin condition, including but not limited to open lacerations or abrasions, hidradenitis, or dermatitis of the treatment area prior to treatment (duration of resolution as per the Principal Investigator's discretion) or during the treatment course.
- History of keloid scarring, abnormal wound healing and /or prone to bruising.
- History of epidermal or dermal disorders (Particularly if involving collagen or microvascularity) including collagen vascular disease or vasculitis disorders
- Subject is unable or unwilling to comply with the study requirements.
- Subject is currently enrolled or has been enrolled within the prior 3 months in a clinical study of any other unapproved investigational drug or device.
- Any other condition that would, in the professional opinion of the investigator, potentially affect the subject's response or the integrity of the data or would pose an unacceptable risk to the subject.

#### **b. Source of Subjects and Recruitment Methods**

The study will be posted on the Rally recruitment website, the Partner's clinical research web page ([rally.partners.org/](http://rally.partners.org/)), to reach an economically and socially diverse population.

### **5. Subject Enrollment**

#### **a. Method of Enrollment**

All subjects will be subject to a telephone prescreening by study staff before scheduling the initial screening visit. All subjects who sign an informed consent form (ICF) and are screened will be documented on a screening log. All subjects who qualify at the screening visit and who are enrolled in the study will be documented on the enrollment log. A note will be made in the source documentation verifying that the subject has willingly signed the ICF prior to participation in any study procedures.

#### **b. Informed Consent Form (ICF)**

A licensed physician investigator will inform the potential study subject of all aspects of the study and answer their questions. Sub-investigators (e.g., nurse practitioner or study staff) may assist in the consent process. If the subject agrees to be a study subject, they will document consent in writing by signing an ICF. Subjects who need more time to decide whether they would like to participate will be given a copy of the consent form and will call if they are interested in participating in the study.

The investigator is responsible for using a consent form that has been approved by the IRB/Partner's HRC and is the most current version. If a new version of the consent form is approved by the IRB/Partner's HRC while a subject is still participating in the study, then the Investigator will inform the subject of the changes and, if the subject agrees to continue study participation, they should sign the updated form.

Written or digital (Adobe E sign) informed consent will be obtained by a licensed physician investigator prior to performance of any protocol-specific procedures.

Only fluent English speakers will be enrolled in the study. Part of the study protocol requires real-time assessment of pain to uncomfortable stimuli. The risks of this study, which does not have any direct benefit for the subject, would outweigh any potential study benefits in this case.

## 6. STUDY PROCEDURES

### a. Study visits and procedures

#### *Screening visit*

Screening visit is expected to last approximately 20 minutes.

During the screening visit, the investigator will discuss with each subject the nature of the study, its requirements, and its restrictions.

The following will be performed to determine eligibility:

- Review of inclusion/exclusion criteria
- Medical history and demographics
- Review of medications

Subjects who qualify for the study will be consented by a licensed physician investigator. Subjects who fulfill all inclusion and exclusion criteria may enroll and begin the Visit 1 procedures that same day.

#### *Visit 1*

Visit 1 is expected to last approximately 1 hour.

The following assessments will be performed during Visit 1:

- Review of eligibility criteria
  - Ring size measurement
- Review of medical history and medications
  - Urine pregnancy test (for female participants of childbearing potential)
- Take blood pressure (2 times before treatment; 2 times after) using a standard hospital owned blood pressure arm cuff device.
- The novel digit cooling device will be turned on and allowed to chill to -3 degrees Celsius prior to the procedure.
- Two fingers (one on each hand) will be pricked during Visit 1: the “control” digit and the “chiller” digit.
  - The first finger to be pricked will be randomized.
  - The pricked fingers will be either the fifth or third digit(s).

- Pricks will be administered using a sterile and disposable McKesson Push-Button 17G or 23G Safety Lancet, bought specifically for this trial.
- Subjects will be instructed on how to report a pain score for each prick. A visual 10-point pain scale will be used (see below).
- The procedure for the “control” digit is as follows:
  - A Beurer oximeter will be used to measure the percent oxygen and pulse rate.
  - A thermal camera will be used to measure the temperature of the finger tip.
  - One prick will be applied to the ventral tip of the “control” digit. A pain score will be reported by the subject.
  - The pricked finger will subsequently be held over a single-use Whatman 903 filter paper. Approximately every ten seconds after the prick, the filter paper will be gently applied to the blood drop to absorb the blood. This will be repeated on new locations of the filter paper until blood flow stops. At least one Whatman 903 filter paper will be used per finger prick. The Whatman 903 filter paper will be imaged.
- The procedure for the “chiller” digit is as follows:
  - A sterile glove will be placed on the “chiller” hand. The top of the fifth or third finger of the glove will be cut and rolled down to the base of the finger to promote venostasis and blood harvesting.
  - A Beurer oximeter will be used to ensure there is not enough blood flow to measure the percent oxygen and pulse rate in the finger.
  - A thermal camera will be used to measure the temperature of the finger tip.
  - A layer of glycerol will be applied circumferentially to the intended treatment area on the “chiller” digit.
  - No more than one minute after sterile glove application, the novel digit cooling device will be applied to the “chiller” digit on the area with glycerol.
  - No more than four minutes after the novel digit cooling device is applied to the “chiller” finger, one prick will be applied to the ventral tip of the “chiller” digit. A pain score will be reported by the subject.
  - The pricked finger will subsequently be held over a single-use Whatman 903 filter paper. Approximately every ten seconds after the prick, the filter paper will be gently applied to the blood drop to absorb the blood. This will be repeated on new locations of the filter paper until blood flow stops. At least one Whatman 903 filter paper will be used per finger prick. The Whatman 903 filter paper will be imaged.
- Post-procedure images will be taken of the tips of the “control” and “chiller” digits.
- A thermal camera will be used to video record the fingers starting with the sterile glove application on the “chiller” finger until the post-procedure images have been collected by an encrypted iPhone 12 Pro.
- Regular video recording with an encrypted iPhone 12 Pro will be done simultaneously.

Wong-baker pain assessment on a visual analog pain scale:

©1983 Wong-Baker FACES Foundation. [www.WongBakerFACES.org](http://www.WongBakerFACES.org)  
Used with permission. Originally published in *Whaley & Wong's Nursing Care of Infants and Children*. ©Elsevier Inc.

- The device will be removed from the digit
- Study staff will document any anticipated side effects or Adverse Events that occur during the study visit.
- A licensed physician investigator will be operating the study device during the procedure.

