## **9. Statistical Analysis**

Pain Scoring Analysis

The Wong-Baker FACES Pain Rating Scale will be used to score subject pain in visit 1.

©1983 Wong-Baker FACES Foundation. [www.WongBakerFACES.org](http://www.WongBakerFACES.org)  
Used with permission. Originally published in *Whaley & Wong's Nursing Care of Infants and Children*. ©Elsevier Inc.

---

Statistical methods

The study is intended to gather empirical data about the pain assessment of the treatment area. Descriptive statistics will be collected to present quantitative descriptions of the pain level comparisons between the two hands.

In order to achieve a power of 0.95 with a p-value < 0.05, a sample size of 16 subjects is needed. This is assuming a standard deviation of 2 on the Wong-Baker Pain Rating scale, which will be used as the primary clinical outcome measure. A two-sided, independent t-test will be used to determine if any significant statistical difference is present between the pain level of each treatment arm using the absolute difference between the control and experimental pain scores.

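### Prick order is randomised, but balance is not specified and order is not used in the analysis: a cheap, minor efficiency gain, best made together with a paired analysis

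*Combined protocol and SAP*

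**What the plan says.** Section 3 describes the design: "This is a self-controlled single-site study of 12 healthy subjects". Section 4 sets the target: "We will recruit and screen up to 20 subjects with the goal of having 12 subjects enroll and complete the study". Under Visit 1 in Section 6, "Two fingers (one on each hand) will be pricked during Visit 1", one as control and one with the device. On sequence, the protocol says only "The first finger to be pricked will be randomized". It gives no allocation list, block size or target ratio.

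Section 9 plans descriptive comparisons between the two hands and then a test: "A two-sided, independent t-test will be used to determine if any significant statistical difference is present", "using the absolute difference between the control and experimental pain scores". Order appears neither as a model term nor as a stratum nor as a check. The sample-size statement reads "In order to achieve a power of 0.95 with a p-value < 0.05, a sample size of 16 subjects is needed", and "This is assuming a standard deviation of 2 on the Wong-Baker Pain Rating scale". It states no effect size, and it does not say whether the SD refers to a single score or to the within-subject difference.

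**The concern.** Two pricks per subject in random order make this a two-period within-subject comparison. The outcome is a self-reported pain score, and the first score is given before the second prick. A systematic difference between first and second prick, from anticipation or from anchoring on the first score, is therefore possible, although the documents neither state nor measure one.

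If there is such an effect, it enters each within-subject difference with a sign that depends on order. Left out of the model, it inflates the error variance. In a single trial of 12 it also moves the point estimate whenever the two orders are unequally represented. The protocol already randomises order, so the information that would remove this noise will exist but is not used.

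**Working it through.** **Inputs.** From the documents: N = 12 completers, SD 2, two-sided 0.05, power 0.95, stated N of 16. Assumed, because not given: device effect (2 points), order effect π (second minus first prick, 0 to 1.5 points), and the meaning of the SD.

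**1. The plan's own figure.** Without an effect size, 16 cannot be reproduced from the stated inputs alone. Solving for the effect by noncentral t at SD 2 and power 0.95 gives 1.93 points (paired, 16 subjects), 2.64 (independent, 16 per arm) or 3.88 (independent, 8 per arm). An effect of 2 points with SD of differences 2 returns exactly 16 in a paired t-test (power 0.962), against 27 per arm in an independent one. That is why 2 points is used below. At n = 12, paired power is 0.883.

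**2. Chance of a lopsided split.** With simple randomisation the number pricked control-first is Binomial(12, 0.5):
- 6:6: 924/4096 = 22.6%
- 8:4 or worse: 2 × (495 + 220 + 66 + 12 + 1)/4096 = 38.8%
- 9:3 or worse: 2 × (220 + 66 + 12 + 1)/4096 = 14.6%

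**3. Effect on the estimate.** Let d = control − chiller = τ + sπ + e, with s = +1 if the chiller finger is first, −1 if the control finger is first, and SD(e) = 2. The unadjusted mean shifts by π × (imbalance)/12. For π = 1 this is 4/12 = 0.33 at 8:4 and 6/12 = 0.50 at 9:3. The standard error without an order effect is 2/√12 = 0.577. Over all randomisations the shift averages zero: the simulated mean is 2.00 for a true 2, and type I error stays near 0.05.

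**4. Effect on power.** Under simple randomisation the variance of d is 4 + π², that is +6%, +25% and +56% at π = 0.5, 1 and 1.5. The unadjusted paired test has noncentrality 2√12/√(4 + π²) with 11 df. The 6:6 design with an order term has 2√12/2 = 3.46 with 10 df, whatever π is. For the independent test, per-score SD 2 and correlation 0.5 are assumed, which gives SD of differences √(4 + 4 − 2 × 0.5 × 4) = 2. Order then adds π²/4 to each arm's variance, about 6% at π = 1.

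| π (points) | Independent t, as written | Paired t, no order term | Paired, 6:6, order term |
|---|---|---|---|
| 0 | 0.70 | 0.88 | 0.88 |
| 0.5 | 0.69 | 0.86 | 0.88 |
| 1 | 0.65 | 0.81 | 0.88 |
| 1.5 | 0.61 | 0.71 | 0.88 |

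The first column is simulated; with correlation 0 it becomes 0.65, 0.64, 0.62 and 0.59. The second and third columns are from noncentral t and agree with simulation.

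**5. Are both parts of the change needed?**
- Balance without the term: at π = 1, power is 0.82 and type I error about 0.03, because the residual SD still contains order while the estimate no longer does.
- Term without balance, no order effect: power is 0.876 at 6:6, 0.867 at 7:5, 0.837 at 8:4, 0.771 at 9:3, 0.644 at 10:2 and 0.410 at 11:1. Weighted by the binomial probabilities: 0.226 × 0.876 + 0.387 × 0.867 + 0.242 × 0.837 + 0.107 × 0.771 + 0.032 × 0.644 + 0.006 × 0.410 ≈ 0.84. Against 0.883 this is a loss of about 4 percentage points.
- Both, no order effect: 0.883 to 0.876, a loss of under 1 point.

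**The case against.** The case for leaving the plan alone has real substance.

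- **Randomised order already gives validity.** This stands. A reader might infer that the device estimate is biased, or that an order effect will be mistaken for a device effect. The documents do not support that: the shift is chance imbalance in either direction, and it averages to zero. The added variance and the shift after a lopsided split are two views of the same error and should not be counted twice. At π = 1 the 9:3 shift (0.50) is still below the standard error (0.577). The conditional view is not empty, though: given a 9:3 split, the unadjusted paired test has type I error of about 9% at π = 1.
- **Balance is not ruled out.** This stands. A reader might infer that allocation will be unbalanced. The protocol says only that order is randomised, and a blocked list would fit that wording. The gap is one of specification.
- **The planned test is not paired.** This stands and matters most for size. The fall from 0.88 to 0.81 is not the loss of the test in Section 9. For that test, a 1-point order effect costs about 4 to 5 points (0.70 to 0.65). Pairing alone moves 0.70 to 0.88 when there is no order effect.
- **The order effect is assumed.** This stands. Nothing in the documents says that one is expected, and 1 to 1.5 points would be 50% to 75% of the only SD stated. At 0.5 points the gain is about 2 points of power.
- **An additive term may miss the mechanism.** This stands in part. If anchoring depends on whether the chilled finger came first, that is an order-by-device (carryover) effect, which the term does not remove.
- **Section 9 is partly descriptive.** True, but it also names a significance test and a power target.

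**Conclusion.** The point holds as a minor, nearly free improvement. Balance is not specified and order is not used, so any order effect stays in the error term. Against an unadjusted paired t-test, balance plus an order term recovers about 2, 7 and 16 percentage points of power at order effects of 0.5, 1 and 1.5 points (0.86, 0.81 and 0.71 to about 0.88). It costs under 1 point if there is no order effect. Against the independent test as written, most of the improvement comes from pairing, and the order term makes sense only alongside that change.

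These sizes rest on an assumed 2-point device effect, SD of differences 2, n = 12, simple randomisation and, for the independent test, correlation 0.5. None of these is settled by the documents except n = 12, and Section 9 itself says 16 are needed.

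**What to change.** 1. In Section 6, state that order comes from a pre-generated list balanced for the final N: 6 control-first and 6 chiller-first if N is 12, and equal halves for whatever N results once 12 and 16 are reconciled. If such a list already exists, say so. It must be in place before enrolment, because balance cannot be restored afterwards.
2. In Section 9, replace the independent t-test with an analysis of the signed within-subject difference, and add an order term coded +1/−1. The intercept is then the order-adjusted device effect, reported with its 95% CI on N − 2 degrees of freedom.
3. Make both changes together, for the reasons in step 5 of the working.
4. State that the model assumes no order-by-device (carryover) effect, and show the differences descriptively by order.

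The cost is one list, one model term and one degree of freedom. No study procedure changes.
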